### Study Population and Sample Size

The eligible patient population is patients age  $\geq 50$  with polypharmacy as defined by  $\geq 5$  medications based on the pre-hospital admission; able to self-consent or has a proxy; home residence within the nine-county radius of VUMC; does not reside in long-term care and is not hospice eligible. All eligible patients will be approached for consent. We anticipate enrolling approximately 144 patients per year, or 576 across all four years of enrollment. Among those, we estimate that 27.5% will either die or become unreachable prior to 90-day follow up. Thus, across all four years of enrollment, 420 patients will contribute measurements at 90 days. Although 567 is the expected enrollment, we conservatively use 420 to estimate the statistical power

associated with our hypotheses based on overall completion rate, rather than enrollment rate, to account for attrition.

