## STATISTICAL CONSIDERATIONS

### Sample Size and Randomization

Figure 1 illustrates the flow of participants through the study and estimated total sample sizes during each study phase based on prior data. The overall effectiveness of the intervention will be evaluated based on the primary outcome measure, which is total medication count. Based on current enrollment rate, we estimate that approximately 144 patients per year will enroll in the study, or 576 across all four years of enrollment. Among those, we estimate that 27.5% will either die or otherwise be lost from the study prior to the 90-day post PAC discharge follow up period. Thus, across all four years of enrollment, an estimated 420 patients will contribute measurements at 90 days. Although 567 is the expected total enrollment, we conservatively use 420 to estimate the statistical power associated with the assessment of overall effectiveness (i.e., overall completion rate) rather than enrollment rate, to account for estimated attrition across all study phases.

Preliminary data is available for the effect of deprescribing on the reduction in the counts of total medications. Our pilot intervention (N=40) was associated with roughly a 50% reduction in the count of total medications from enrollment to hospital discharge, whereas a roughly 25% reduction was observed in the control group receiving routine hospital care. Using these preliminary data and mixed-effects Poisson regression methods, we implemented a simulation-based power analysis wherein we assumed that this effect would be attenuated by 20% at SNF discharge, and again by 20% at the 90-day follow up. Using a sample size of 420, there is greater than 95% power to detect a 50% versus 25% reduction in total medications. There is approximately 90% power to detect a 30% versus 25% reduction in total medications, and 80% power to detect a 27.5% versus 25% reduction in total medications. Thus, the target sample size provides some protection against effects that are substantially smaller than that observed in our preliminary data.

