## Outcomes

Hypotheses 1a-1b: The effect of the intervention on the total number of medications, PIMs, and medications associated with geriatric syndromes at hospital discharge, SNF discharge, and at 90-days following SNF discharge will be assessed using mixed effects Poisson regression, allowing for overdispersion (more or less variability than is expected under the Poisson regression model), and adjusting for measurement time point (as a categorical covariate) and the total number of medications at participant enrollment. The within-subject correlation among repeated measurements will be modeled using a random intercept term, indexed by subject. The intervention effect at each time point will be summarized using a Wald-type 95% confidence interval. Statistical significance will be indicated if the 95% confidence interval excludes the value zero (i.e., the Poisson regression intervention effect under the null hypothesis). Model fit will be assessed by examining the associated Pearson residuals and using other graphical methods. Alternative regression techniques may be used in the case of poor fit, for example, negative-binomial regression.

Hypothesis 1c: The effect of intervention on the anticholinergic and sedative medication drug burden scores at hospital discharge, SNF discharge, and 90-days following SNF discharge will be assessed using linear mixed effects regression, adjusting for measurement time point, and using a random intercept term indexed by subject. Intervention effects will be summarized using 95% confidence intervals. Model fit will be assessed using residual diagnostics and graphical methods. Due to the constrained nature of the score values (0-1 for anticholinergic and sedative drug burden scores), an alternative method may be required, such a ‘beta’ regression, which is suitable when such scores frequently occur at a boundary (0 or 1).

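### The power quoted at N=420 names no contrast, its 90% and 80% figures cannot belong to one test, and it does not describe the visit-by-visit tests planned

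*Combined protocol and SAP*

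**What the plan says.** Sample Size and Randomization bases the power on a simulation: "Using these preliminary data and mixed-effects Poisson regression methods, we implemented a simulation-based power analysis". The pilot effect is roughly a 50% versus 25% reduction in total medications from enrollment to hospital discharge, and "we assumed that this effect would be attenuated by 20% at SNF discharge, and again by 20% at the 90-day follow up". Three results follow, all at N=420:

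- Pilot-sized effect, 50% against 25%: power above 95%.
- Smaller effect, in the plan's words: "There is approximately 90% power to detect a 30% versus 25% reduction in total medications".
- Smallest effect, 27.5% against 25%: power of 80%.

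The paragraph ends by saying that the target size gives a degree of protection against effects well below the pilot's.

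On what the power refers to, the same section says "we conservatively use 420 to estimate the statistical power associated with the assessment of overall effectiveness". The number itself is the count expected at the last visit; the précis says that "420 patients will contribute measurements at 90 days". No time point, enrollment mean, random-intercept variance or dispersion is given. Nor does the text say whether the smaller scenarios are effects before or after attenuation.

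For Hypotheses 1a-1b the Outcomes section states: "The intervention effect at each time point will be summarized using a Wald-type 95% confidence interval". The visits are hospital discharge, SNF discharge and 90 days after SNF discharge. Significance is judged by whether the interval excludes zero. No pooled test over visits is specified.

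**The concern.** A power figure is useful only if the reader knows which test it belongs to. Here the analysis has three tests per count outcome, the simulation shrinks the effect from one visit to the next, and a single power is printed for each effect size. Because 420 is defined by 90-day completers, a reader is likely to attach the printed power to the 90-day result.

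The printed pair also looks wrong on its face. Halving the difference from 5 to 2.5 percentage points costs only 10 points of power.

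At stake is the reading of a null result. Hypotheses 1a to 1c all include 90 days after SNF discharge. If the true effect there is small, a non-significant interval could be taken as evidence that deprescribing did not last, when the test may have had little chance of detecting it.

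**Working it through.** **Inputs.** 420 patients, 210 per arm (1:1 allocation); two-sided 5% (95% Wald interval); attenuation 0.80, then 0.80 × 0.80 = 0.64 (all from Statistical Considerations). The enrollment mean B is not stated. Preliminary Data gives 12.6 and 6.5 deprescribed drugs, and the power paragraph gives 50% and 25% reductions, so B = 12.6/0.50 = 25.2 or 6.5/0.25 = 26.

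**Step 1: do the 90% and 80% agree?** This needs no outside input.

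- Log effects: |ln(0.70/0.75)| = 0.0690 and |ln(0.725/0.75)| = 0.0339; ratio 2.04.
- Effect/SE needed: 1.96 + 1.28 = 3.24 for 90%; 1.96 + 0.84 = 2.80 for 80%; ratio 1.16.
- If 30% vs 25% has 90%: 3.24/2.04 = 1.59, and Φ(1.59 − 1.96) = about 36% for 27.5% vs 25%.
- If 27.5% vs 25% has 80%: 2.80 × 2.04 = 5.70, and Φ(5.70 − 1.96) = 99.99% for 30% vs 25%.

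The SE differs by only about 1% between the two scenarios, so it cannot close the gap.

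**Step 2: can the printed 90% be reproduced?** For a single visit, SE = √[(1/μc + 1/μi + 2τ²)/210], with μc = 0.75B, μi = (1 − r)B and τ² the residual between-patient variance. Power = Φ(|log ratio|/SE − 1.96). At B = 25.2, r = 0.30, τ² = 0:

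- μc = 18.9, μi = 17.64, SE = √(0.1096/210) = 0.0228.
- 0.0690/0.0228 = 3.02; power 85.5%. At B = 26 it is 86.6%.

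For an average effect over three visits, the effect is multiplied by (1 + 0.8 + 0.64)/3 = 0.813 and the SE is about √[((1/μc + 1/μi)/3 + 2τ²)/210].

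| Test | B, τ² | 30% vs 25% | 27.5% vs 25% |
|---|---|---|---|
| Single visit, no attenuation | 25.2-26, 0 | 86-87% | 32-33% |
| Average of three visits | 25.2-26, 0 | 99% | 56-57% |
| Average of three visits | 25.2-26, 0.01 | 93% | 39-40% |
| Average of three visits | 15, 0 | 91% | 37% |

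Some settings come near 90% for the first effect. None gives 80% for the second alongside it.

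**Step 3: power of each planned test.** Here 30% vs 25% is the hospital-discharge effect, r = 0.25 + 0.05 × (1, 0.80, 0.64) = 0.300, 0.290, 0.282, and τ² = 0.

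| Visit | Log effect | Power, B = 25.2 | Power, B = 26 |
|---|---|---|---|
| Hospital discharge | 0.0690 | 85.5% | 86.6% |
| SNF discharge | 0.0548 | 67.3% | 68.6% |
| 90 days | 0.0436 | 48.5% | 49.7% |

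Attenuating on the log scale gives 49.4-50.6% at 90 days. Simulated trials gave 49-52%.

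**Step 4: how far the 90-day figure moves.**

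- Residual between-patient SD (assumed) 0.2 or 0.3 on the log scale: about 31% or 22%.
- Control mean of 14, the hospital-discharge count in Overview and Objectives (B = 14/0.75 = 18.7): 38%.
- 30% vs 25% already attenuated: about 86%, or about 66% with SD 0.2.
- Underdispersed counts: if drugs are only removed from the enrollment list (binomial thinning), 96-97% at B = 25.2-26 and 79% at B = 14.
- Underdispersed, with new drugs equal to an assumed 10-20% of the enrollment count: 83-70% at B = 25.2.

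**Step 5: the pilot-sized effect.** 50% vs 25% has at least 99.9% power at all three visits, for τ² up to 0.149.

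**The case against.** The strongest reply is that the plan never claims 90% power for the 90-day test. It ties the power to overall effectiveness, and 420 is a cautious sample size that allows for attrition, not a choice of visit. The model lists time point as a covariate and spells out no interaction, so a common effect over visits may be what was simulated; such an effect can reach about 90%. This stands, and it rules out saying that the printed 90% should have read 50%.

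Two further points stand. The mean of 25 to 26 is inferred, and the pilot's deprescribed drugs may include dose reductions, which do not lower the count, so the true mean may be smaller. And about 50% is not a ceiling: the Outcomes section allows less variability than Poisson, which would raise power. Against that, the power analysis itself is described as mixed-effects Poisson, which cannot generate variance below Poisson, and the Limitations paragraph expects drugs to be added after discharge, so pure thinning is too favourable.

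Rescaling the printed figures settles nothing. Multiplying the required 3.24 by 0.64 gives 54.6% at 90 days. Starting from the 80% figure instead, 5.70 × 0.64 = 3.65 gives 95.4%.

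None of this rescues the pair. Step 1 holds for a single-visit or pooled Wald test, whatever the mean or variance, provided both scenarios share them. Nor does the pooled reading supply a match with the analysis, which reports the effect at each visit and specifies no pooled test.

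**Conclusion.** The point holds in two parts of different strength.

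- **Firm.** About 90% for 30% vs 25% and 80% for 27.5% vs 25% cannot both be the power of one test at N=420. If the first is right, the second is about 36%. This rests only on the printed percentages and a two-sided 5% Wald test.
- **Conditional.** The printed figures do not describe the three tests planned. With Poisson variance, B of 25 to 26, no between-patient variance and 30% vs 25% read before attenuation, power is about 86%, 67-69% and 50% at the three visits. The pre-attenuation reading is the more natural one, since the text attenuates an enrollment-to-hospital-discharge effect, but the document does not state it.

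A reader might infer that 90-day power is at most 50%, or that the plan misreports its 90-day power as 90%. The documents support neither: they fix no mean, variance or dispersion, and they never assign the 90% to a visit. A reader might also infer that the trial is too small. That does not follow either, because the effect seen in the pilot stays above 95% power at every visit. What is unsupported is the assurance about much smaller effects.

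**What to change.** Rerun the existing simulation and rewrite the power paragraph under Sample Size and Randomization so that it:

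- gives power for each contrast tested in the Outcomes section, including 90 days at N=420; if an overall effect is meant, define that test in Outcomes too;
- states the assumed enrollment mean, random-intercept variance and dispersion;
- says whether each effect size is before or after attenuation, and on which scale the attenuation acts;
- corrects the 90%/80% pair;
- limits the closing claim of protection to the contrasts and effect sizes that the rerun supports.

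The cost is a rerun and one reworded paragraph. Enrollment does not change. The downside is that the stated power for small effects will look less favourable.

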### Interim analyses and Stopping Rules

Interim analyses will be conducted to evaluate safety endpoints but will not be conducted to evaluate conditional power (futility) or to assess efficacy.

Safety is evaluated by examining group differences in death and serious adverse events semi-annually in conjunction with scheduled DSMB meetings to evaluate the safety of the study intervention, and the associated risk-to-potential benefit ratio. The Principal Investigators will address study efficacy only at the end-of-study, and thus will not consider terminating the trial early on the basis of conditional power (futility) or evidence of efficacy. This is because firm evidence will be required to change current clinical practice, and because trials that have stopped early for efficacy often report implausibly large effect sizes (and therefore should be considered with skepticism). At the conclusion of each DSMB meeting, the Board should take into account the statistical evidence (as summarized by the relative hazard of safety endpoints and the corresponding 95% confidence interval) as well as practical and clinical considerations to make one of the following recommendations based on safety:

1. Suspend enrollment due to safety concerns secondary to study intervention including:

- a. A difference in all-cause mortality between patients randomized to the deprescribing intervention versus usual care such that the DSMB deems the difference to be study-related and excessive.
  - b. A difference in drug related SAEs between patients randomized to the deprescribing intervention versus usual care such that the DSMB deems the difference to be study-related and excessive.
2. Continue enrollment

## Outcomes

Hypotheses 1a-1b: The effect of the intervention on the total number of medications, PIMs, and medications associated with geriatric syndromes at hospital discharge, SNF discharge, and at 90-days following SNF discharge will be assessed using mixed effects Poisson regression, allowing for overdispersion (more or less variability than is expected under the Poisson regression model), and adjusting for measurement time point (as a categorical covariate) and the total number of medications at participant enrollment. The within-subject correlation among repeated measurements will be modeled using a random intercept term, indexed by subject. The intervention effect at each time point will be summarized using a Wald-type 95% confidence interval. Statistical significance will be indicated if the 95% confidence interval excludes the value zero (i.e., the Poisson regression intervention effect under the null hypothesis). Model fit will be assessed by examining the associated Pearson residuals and using other graphical methods. Alternative regression techniques may be used in the case of poor fit, for example, negative-binomial regression.

Hypothesis 1c: The effect of intervention on the anticholinergic and sedative medication drug burden scores at hospital discharge, SNF discharge, and 90-days following SNF discharge will be assessed using linear mixed effects regression, adjusting for measurement time point, and using a random intercept term indexed by subject. Intervention effects will be summarized using 95% confidence intervals. Model fit will be assessed using residual diagnostics and graphical methods. Due to the constrained nature of the score values (0-1 for anticholinergic and sedative drug burden scores), an alternative method may be required, such a ‘beta’ regression, which is suitable when such scores frequently occur at a boundary (0 or 1).

Hypothesis 2a: The prevalence and severity of geriatric syndromes will be analyzed at each time point following SNF discharge. The effects of intervention on the prevalence of each type of geriatric syndrome will be assessed using mixed-effects logistic regression, adjusting for measurement time point (categorical). The severity of each geriatric syndrome is measured on an ordinal scale. Thus, severity will be analyzed using mixed-effects proportional odds logistic regression, also adjusting for measurement time point. For either method, the correlation among repeated measures will be modeled using a random intercept term indexed by subject. The effects of intervention at each time point will be summarized using the odds ratio with Wald-type 95% confidence intervals. Statistical significance will be indicated when the 95% confidence interval excludes the value one (i.e., null hypothesis value for both types of logistic regression). Model fit diagnostics and alternative analysis strategies will be considered as described for Hypotheses 1a-1c.

Hypothesis 2b: Patient medication adherence will be measured using selected questions from the ARMS, based on an ordinal scale. Functional health status will be measured using the VES-13 total score, which is also an ordinal outcome. The effects of intervention on these outcomes will be assessed at 7 and 90-days following SNF discharge using mixed-effects logistic regression or proportional odds logistic regression in a manner that is analogous to that described for Hypothesis 2a.

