## **STUDY PROCEDURES**

Data collection includes patient descriptive data as well as three groups of outcomes: geriatric syndromes, medications and health status, safety and healthcare utilization. Table 1 shows a summary of the study timepoints along with the corresponding assessments. Upon enrollment, hospitalized participants complete interviewer-administered questionnaires, which require approximately 45 minutes per participant. Following

discharge to SNF, facility staff is required to assess all residents upon SNF admission and discharge using the standardized Minimum Data Set (MDS), which includes an assessment of these same geriatric syndromes using similar scales. The baseline hospital questionnaires are repeated by research staff via telephone 7-10 days after PAC discharge and in-person in the participant’s place of residence at 90-days after PAC discharge. *(During the COVID-19 pandemic, the VUMC IRB allowed the 90-day visits to be completed as telephone calls or using Vanderbilt’s HIPAA compliant video technology to limit exposure risks to both participants and staff).* A telephone interview is also conducted at 60-days post SNF discharge to assess medications and health-related measures. If a participant has a follow-up outpatient visit scheduled at VUMC during any of these time frames, an effort is made to conduct the interview in-person during that visit, if they prefer. For assessments completed in-person, the study team provided hearing and visual aids if necessary (e.g., hearing amplifiers and large font printed response cards with Likert scale categories). Both the intervention and control groups will be monitored using the same data collection schedule and measures. All interview assessments are completed by trained research personnel on our multidisciplinary team which includes a social worker, geriatric nurse practitioners, clinical pharmacists, geriatrician, hospitalist, and psychologist.

In the event a participant is unable to complete assessments due to delirium or cognitive impairment, their designated surrogate or caregiver (e.g., child, spouse, assisted living facility nurse) is interviewed to complete assessments which are validated for use with surrogates. Assessments that can be completed by surrogates include the ICIQ (urinary incontinence), Determine, falls, pressure ulcers, medication history, and demographics.

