Drug Burden Index (DBI): A DBI score is calculated separately for anticholinergic (DBIAC) and sedative medications (DBIS), which have been strongly linked to functional impairment, falls and delirium. The drug burden is the sum of each individual anticholinergic/sedative medication's prescribed daily dose divided by the sum of the minimum effective dose (as estimated by the FDA minimum recommended dose) and the patient's daily dose. The DBI includes over-the-counter medications. We will calculate the DBI at the time of randomization, hospital discharge, PAC discharge, and all follow-up timepoints. Importantly, the DBI captures reductions in dose, even when total number of medications is not reduced.

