## **Secondary Outcomes - Geriatric Syndromes, Medication Adherence, Functional Health Status**

**Delirium:** The Brief Confusion Assessment Method (bCAM) is a brief screening tool for delirium and has been validated among hospitalized, older patients. If the participant screens positive for delirium, no other participant interviews are conducted at that time. Research personnel continue to re-assess delirium daily during hospitalization; and, when the participant screens negative for delirium via the bCAM, the remaining assessments are administered to the participant. If delirium continues throughout the hospital stay or the participant is otherwise unable or unwilling to complete the assessments, the surrogate is approached for a subset of the geriatric syndrome assessments (i.e., incontinence, nutrition and fall history). The bCAM is not repeated by research personnel at 7-day follow-up because it has limited validity when administered via the telephone; thus, it is repeated only at 90-day follow-up during the in-person home visit. Additionally, PAC personnel use the CAM (i.e., the Confusion Assessment Method, [CAM]), which is a modified version of the bCAM, to assess delirium during the PAC stay via the MDS assessment.

**Cognitive Impairment:** The Brief Interview for Mental Status (BIMS) is a short, validated assessment of cognitive impairment with a total score range from 0 to 15 (0-7: severe impairment; 8-12: moderate impairment; 13-15: cognitively intact). The BIMS is routinely used in the SNF care setting as part of required MDS assessments for all SNF patients upon admission and discharge and following a hospitalization event.

**Depression:** The Patient Health Questionnaire (PHQ) is a validated tool to assess depression symptoms and severity. Each item is scored from 0 (“not at all”) to 3 (“nearly every day”) to yield a total score range from 0 (no depressive symptoms) to 27 (severe depression). In the event that a participant reports severe depression or thoughts of self-harm, the study team elicits more information to evaluate their immediate safety then contacts the primary treatment team to address this with the participant. The PHQ-9 is routinely used in the SNF care setting as part of required MDS assessments.

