## Data Analyses

Missing Data: We have extensive preliminary data describing attrition due to mortality which should not differ between the intervention and control groups. However, we cannot exclude the possibility that missing data will be associated with intervention. We will examine the incidence of missing data by group. If imbalances are found, we will implement a series of sensitivity analyses, using multiple imputations, to assess the degree of bias that might be induced by missing data.

Randomization, intent-to-treat, and safety outcomes: Participants will be assigned to the usual care control group or the intervention group in a completely randomized fashion (i.e., without blocking or stratification). The effectiveness of randomization will be assessed by summarizing the balance of baseline demographic and clinical factors across randomization groups. The sample mean, standard deviation, and five-number summary will be used to summarize continuous variables. The count and proportion will be used to summarize categorical variables. All randomized patients who complete Phase 2 (i.e., discharged to a partner SNF) will be included in analyses. We will implement both intent-to-treat and per-protocol analyses.

Repeated measures: Barring study withdrawal or death, each participant will be assessed at multiple time points. We anticipate that such repeated measurements will exhibit correlations across time points. Our statistical plan takes full advantage of this information by using a mixed-effects framework for each analysis. In the event that a mixed-effects technique cannot be implemented, an alternative method will be used and the standard errors of effect estimates will be adjusted using the Huber-White ‘sandwich’ method.

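### Every outcome model except the one for total medication count leaves out that outcome's own baseline value, although all of these baselines are scheduled; the comparisons stay valid but lose precision and power that need no new data to recover

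*Combined protocol and SAP*

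**What the plan says.** All the models are in the Outcomes section of the combined protocol and SAP.

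- **Hypotheses 1a-1b** (total medications, PIMs, syndrome-related medications): one mixed-effects Poisson model serves all three counts, adjusted for time point "and the total number of medications at participant enrollment". The response visits are hospital discharge, SNF discharge and 90 days.
- **Hypothesis 1c** (DBI): analysed "using linear mixed effects regression, adjusting for measurement time point, and using a random intercept term indexed by subject", at the same three visits.
- **Hypothesis 2a** (syndromes): prevalence is analysed by "mixed-effects logistic regression, adjusting for measurement time point (categorical"; severity uses a proportional odds version with the same adjustment. Only visits after SNF discharge are modelled.
- **Hypothesis 2b** (ARMS, VES-13): "The effects of intervention on these outcomes will be assessed at 7 and 90-days following SNF discharge", by analogy with 2a.

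Table 1 marks every one of these measures at the baseline hospital visit. For DBI, the text under Primary Outcomes - Medications adds: "We will calculate the DBI at the time of randomization, hospital discharge, PAC discharge, and all follow-up timepoints". The only other planned use of baseline data is descriptive, under Data Analyses: "The effectiveness of randomization will be assessed by summarizing the balance of baseline demographic and clinical factors across randomization groups".

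**The concern.** Only total medication count is adjusted for its own starting value. Elsewhere the baseline enters neither as a covariate nor as a response row, because every modelled visit comes after baseline. The random intercept does not fill the gap: it describes correlation among the follow-up visits and cannot use a measurement that is not in the model.

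Under 1:1 randomization the comparisons are still valid on average, and their intervals already allow for chance imbalance. What is lost is precision for DBI, a smaller amount for the two medication counts, and power for Aim 2. Any chance difference between arms at baseline also stays in the estimates. This matters because the plan states power only for total medication count, while its section on the importance of the knowledge to be gained presents the effect on geriatric syndromes as the question the trial will answer. The Study Design section also describes the primary outcomes as change, yet only total count is modelled relative to its own baseline.

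**Working it through.** **Inputs.** From Sample Size and Randomization: 576 enrolled, 27.5% lost, 420 contributing at 90 days, allocation 1:1. The completer figure reproduces closely: 576 × (1 − 0.275) = 417.6. From Overview and Objectives: means of 14 medications at hospital discharge and 5.9 syndrome-related discharge medications per patient. The documents give no baseline-to-follow-up correlation r, so r is an assumption below.

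**DBI (linear model, one visit).** Adding the own baseline multiplies the variance of the treatment contrast by 1 − r². The equivalent unadjusted sample is 420 / (1 − r²).

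| r | 1 − r² | Equivalent N | An 80% power becomes |
|---|---|---|---|
| 0.3 | 0.91 | 462 | 83.6% |
| 0.5 | 0.75 | 560 | 89.9% |
| 0.7 | 0.51 | 824 | 97.5% |

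In simulation (N = 420, 1,500 runs per setting), type I error was 4.5-5.1% without the baseline and 4.1-5.4% with it. That supports reading this as an efficiency point.

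**Chance imbalance.** With 210 per arm, the baseline difference between arms has SD √(2/210) = 0.098 outcome SDs. For a continuous score a fraction r passes into the unadjusted estimate: 0.3 × 0.098 = 0.03 to 0.7 × 0.098 = 0.07 SD.

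**Syndrome-related medications.** Total count is already in the model, so only the further gain counts.

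- Simulation: Poisson-lognormal counts with means 5.9 syndrome-related and 14 − 5.9 = 8.1 other; log-rate SD 0.25, 0.4 or 0.6; correlation between the two rates 0.2 or 0.6; quasi-Poisson at 90 days; 1,000 runs each. Variance fell by 0.5, 2.2, 3.7, 9.9, 11.8 and 24.1%.
- Partial correlation: let a be the correlation of the outcome with its own baseline, b its correlation with baseline total count, and c the correlation between the two baselines. The further reduction is (a − bc)² / [(1 − b²)(1 − c²)]. With a = 0.5, b = 0.4, c = 0.6 it is 0.26² / (0.84 × 0.64) = 13%. With a = 0.7 it is 0.46² / (0.84 × 0.64) = 39%.

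The documents give no mean PIM count, so PIMs were not simulated separately.

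**Binary syndrome at 7 and 90 days.** Random-intercept logistic model with treatment-by-visit terms, N = 420, prevalence 0.42-0.45, 400 runs (Monte Carlo error of power about 2.5 points).

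| Patient SD (logit) | True log OR | SE of 90-day log OR, without → with baseline | Power |
|---|---|---|---|
| 1 | −0.5 | 0.247 → 0.244 | 50 → 51% |
| 2 | −0.7 | 0.336 → 0.308 | 56 → 64% |
| 3 | −0.95 | 0.448 → 0.377 | 60 → 76% |

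**Binary syndrome at a single visit.** This applies to delirium by bCAM, since "it is repeated only at 90-day follow-up during the in-person home visit". Ordinary logistic regression, conditional log OR −0.6, −0.8 and −1.0, 3,000 runs.

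| Patient SD | Mean log OR | SE | Power |
|---|---|---|---|
| 1 | −0.50 → −0.52 | 0.206 → 0.209 | 68 → 69% |
| 2 | −0.49 → −0.58 | 0.203 → 0.222 | 68 → 75% |
| 3 | −0.47 → −0.66 | 0.201 → 0.242 | 64 → 78% |

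Here the standard error rises. Power improves because the odds ratio becomes conditional on baseline and moves further from 1.

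**The case against.** The strongest reply is that nothing is wrong: the comparisons are valid, the measure of overall effectiveness is already baseline-adjusted, and no stated power figure changes. That is accepted, and it limits the point to a recommended improvement.

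Four more specific objections bear on its size.

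- **Correlation may be low.** Baseline is taken during acute illness and the intervention aims to change medications. At r = 0.1 or 0.2 the DBI variance falls by only 1% or 4% (equivalent N 424 or 438). The 1 − r² rule is also a linear-model result, and the plan allows beta regression for DBI.
- **Syndromes may be rarer than assumed.** In single-visit simulations with the same patient SDs and effects (2,000 runs), a 25% prevalence gives power 58 → 58%, 60 → 65% and 53 → 66%. At 10% it gives 31 → 31%, 34 → 37% and 32 → 39%.
- **Some baselines will be missing.** Under Study Procedures, "Assessments that can be completed by surrogates include the ICIQ (urinary incontinence), Determine, falls, pressure ulcers, medication history, and demographics". BIMS, PHQ-9, the pain inventory, ARMS and VES-13 are not on that list. Interviews wait until the delirium screen is negative, and the plan does not say whether they always precede randomization. With 25% of baselines assumed missing, and mean fill plus an indicator, power for a linear outcome still reached 83.4, 85.8 and 94.2% at r = 0.3, 0.5 and 0.7, against about 80% unadjusted.
- **Not everything was sized.** ARMS, VES-13 and the ordinal severity models were not simulated. ARMS has no 7-day assessment in Table 1, so an analysis at 7 and 90 days would use one visit only.

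These stand as limits on the size of the gain. None makes adjustment harmful, provided patients with a missing baseline are kept.

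**Conclusion.** The concern holds. The plan omits the own baseline for PIMs, syndrome-related medications, both DBI scores, every geriatric syndrome, ARMS and VES-13, although each is scheduled at baseline. The consequence is lost efficiency, with no bias from this source; the total-count analysis is untouched.

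The omission is certain and its size is not. For DBI, the variance reduction is 9-49% if r lies between 0.3 and 0.7, and close to nothing if r is near zero. For syndrome-related medications, the gain beyond total count is about 1-24% in the count simulation; the partial-correlation calculation, with higher assumed correlations, gives 13-39%. For the syndromes, the power gain runs from negligible to moderate, depending on prevalence and on how strongly baseline status predicts follow-up. The change should be made, but the trial's validity does not depend on it. This conclusion concerns the missing covariate only, not attrition or the restriction of the analysis to patients discharged to a partner facility.

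**What to change.** Before outcome data are unblinded, amend the Outcomes section as follows.

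1. Add each outcome's own baseline as a covariate: PIM count, syndrome-related medication count, anticholinergic DBI, sedative DBI, status or severity of each syndrome, ARMS and VES-13.
2. Keep total medication count at enrollment in the PIM and syndrome-related medication models.
3. Use only values recorded before randomization.
4. Fix the rule for missing baselines in advance (mean fill or a missing-baseline indicator), so that patients with persistent delirium or surrogate-only assessment are not dropped.
5. State that the adjusted odds ratios for Hypotheses 2a and 2b are conditional on baseline.

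The cost is a few sentences of SAP wording and slightly more programming, with no new data and no extra patients. Specifying this now also avoids the appearance of selective adjustment that would follow if baselines were added after results were seen.
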